Subjects Switching from Tetrabenazine (Switch): Subjects who are currently receiving an FDA approved dose of tetrabenazine (TBZ) that is providing a therapeutic benefit for chorea control associated with HD will be eligible to participate in the study. Subjects in this cohort will undergo a full screening evaluation within 30 days of the Baseline assessment prior to switching to SD-809 ER. See Schedule of Events A. These subjects will be converted from their TBZ regimen to an SD-809 ER regimen that is predicted to provide comparable exposure to total ($\alpha+\beta$)-dihydro-tetrabenazine (α - and β -HTBZ). Subjects will continue taking their TBZ regimen through midnight of Day 0 and then directly switch to their assigned SD-809 ER regimen the next morning. The dose of SD-809 ER may be adjusted weekly (upward or downward) in increments of 6 mg per day (6 mg/day or 12 mg/day after a total daily dose of 48 mg is reached) to identify a dose level that adequately controls chorea, the subject experiences a protocol defined "clinically significant" adverse event (defined as related to study medication and either a) moderate or severe in intensity or b) meets the criteria for a Serious Adverse Event [SAE])¹; or the maximal allowable dose is reached. If a subject experiences a "clinically significant" AE attributable to SD-809 ER, the investigator will determine if a dose reduction or suspension is necessary. The investigator, in consultation with the subject and caregiver, will determine when an adequate level of chorea control has been achieved. Subjects will have a clinic visit at Week 1 and a telephone contact at Week 2, in order to evaluate safety and establish an optimal dose. Although subjects will enter the Long term treatment period after Week 2, dose adjustment (upward or downward) may continue through Week 4 to optimize dose level. Additional dose adjustments may be made after Week 4 if clinically indicated.

Subjects Enrolled from the SD-809-C-15 Study (Rollover): Subjects who have successfully completed Study SD-809-C-15 may be eligible to rollover directly into this study after they complete a one week washout and the Week 13 evaluation of Study SD-809-C-15. To reduce subject burden, after obtaining capacity assessment (if applicable)/informed consent/assent and

¹ See Section 7 for evaluation of AEs regarding severity, relationship to study drug and definition of SAE.

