8.3 Safety Analyses

Safety and tolerability will be assessed throughout the study by monitoring the following parameters:

 • Adverse events (AEs) • Clinical laboratory tests • Physical examination • Vital signs • 12- lead ECGs • Epworth Sleepiness Scale (ESS) 	
 • Columbia Suicide Severity Rating Scale (C-SSRS) • Unified Huntington’s Disease Rating Scale (UHDRS) • Swallowing Disturbance Questionnaire (SDQ) • Unified Parkinson’s Disease Rating Scale (UPDRS), dysarthria item • Barnes Akathisia Rating Scale (BARS) • Hospital Anxiety and Depression Scale (HADS) • Montreal Cognitive Assessment (MoCA©)
---	--

Safety data will be summarized descriptively for the overall population and based on prior treatment [SD-809 ER or placebo (Rollover subjects) or tetrabenazine (Switch subjects)]. Descriptive statistics will be calculated for quantitative data and frequency counts and percentages will be provided for categorical data. Descriptive statistics of change-from-baseline for Rollover subjects will utilize the Baseline from Study SD-809-C-15 (C-15 Baseline) and the Baseline from the present study (C-16 Baseline), as appropriate, and will be specified in the Statistical Analysis Plan.

The nature, frequency, and severity of adverse events will be tabulated for all subjects combined and by treatment. Baseline, within study, end of study, and change-from-baseline values for clinical laboratory evaluations and vital signs will be summarized as appropriate.

Treatment-emergent adverse events and laboratory, vital sign, and ECG parameters will be summarized. In addition, change from baseline will be summarized for laboratory and vital sign parameters. Shift tables will be provided for clinical laboratory results. ECG results will be classified as normal and abnormal and summarized.

8.4 *Safety Endpoints*

The following safety endpoints will be assessed:

- Incidence of adverse events (AEs), serious AEs, severe AEs, drug related AEs, AEs leading to withdrawal during the following periods:
 - Overall
 - During titration in Rollover subjects (up to 8 weeks)
 - During dose adjustment in Switch subjects (up to 4 weeks)
 - During long term treatment
- Observed values and changes from baseline in clinical laboratory parameters (hematology, chemistry, and urinalysis)
- Observed values and changes from baseline in vital signs
- Observed values in ECG parameters and abnormal findings

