Subjects Enrolled from the SD-809-C-15 Study (Rollover): Subjects who have successfully completed Study SD-809-C-15 may be eligible to rollover directly into this study after they complete a 1-week washout period and the Week 13 evaluation of Study SD-809-C-15. To reduce subject burden, the Week 13 evaluation will provide some Baseline data for the present study. Additional evaluations required as part of the SD-809-C-16 study may be completed on the same day as the Week 13 visit of the SD-809-C-15 study after SD-809-C-16 informed consent/assent is obtained. If subjects are unable to enroll at the Week 13 visit they will have up to 3 weeks to complete the additional evaluations for Baseline or the subject will not be eligible to enroll in this study. In addition, following informed consent/assent, prior data from Study SD-809-C-15 can be used in this study as part of the subject’s medical history information.

As Rollover subjects will have discontinued study drug (SD-809 or placebo) for at least 1 week at completion of the SD-809-C-15 study, they will undergo titration on SD-809. During titration, the Investigator, in consultation with the subject and caregiver, will determine when an adequate level of chorea control has been achieved. The dose of SD-809 may be adjusted (upward or downward), in increments of 6 mg per day (each week) (6 mg/day or up to 12 mg/day after a total daily dose of 48 mg is reached), until there is adequate control of chorea, the subject experiences a protocol defined “clinically significant” adverse event, as outlined above, or the maximal allowable dose is reached. If a subject experiences a “clinically significant” AE attributable to SD-809, the Investigator will determine if a dose reduction or suspension is necessary. Although subjects will enter the long-term treatment period after Week 2, titration may occur through Week 8 to optimize dose level. Additional dose adjustments may be made after Week 8 if clinically indicated.

Long-Term Treatment Period: During long-term treatment, further dose adjustments of SD-809 may be made, if necessary, but not more often than weekly. Dose adjustments should be based on all available information including the subject's and caregiver's reports of adverse events and chorea control, information from rating scales, and all safety evaluations. The Long-Term Treatment Period will continue until SD-809 becomes commercially available in the U.S.

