- 18 For subjects requiring an Unscheduled Clinic Visit for any reason, assessments denoted with X should be performed; all other assessments are as indicated at Investigator's discretion (see Section 6.5 of the protocol).

Table 2: SCHEDULE OF EVENTS B – SUBJECTS *ROLLING OVER* FROM SD-809-C-15

| Study Week → | Screening | | Long Term Treatment | | | | | | | | | | Follow up | | Unscheduled | |
|--------------------------------------|-----------------------------|-----|---------------------|----|----------------|----|----------------|----|----|----------------|------------------|-----------|-----------|-----|------------------|----------------|
| | Baseline‡ | 1 | 2 | 3 | 4 | 5 | 8 | 15 | 28 | 28 + q13 wks | End of Treatment | 1 wk FU | 4 wk FU | | | |
| Visit Window (days) → | +3 | ± 1 | | | | | | | | | | | | | n/a | |
| Visit → | Prior Data from Study C-15† | V1 | T1 | V2 | T2 | V3 | T3 | V4 | V5 | V6 | Vx ⁹ | End Tx/ET | FU | FFU | UV ¹⁰ | UTC |
| Activity Visit type → | V | TC | V | TC | V | TC | V | V | V | V | V | V | V | TC | V | TC |
| Evaluate/Adjust Dose | | X | X | X | X | X | X | X | | | | | | | X | X ³ |
| Evaluate Capacity for consent | X§ [#] | | | | | | | | | | | | | | | |
| Informed Consent/Assent | X§ | | | | | | | | | | | | | | | |
| Research Advance Directive†† | X§ | | | | | | | | | | | | | | | |
| Screening/Demographics | X | | | | | | | | | | | | | | | |
| Selection Criteria | X | | | | | | | | | | | | | | | |
| Update Medical History | X | | | | | | | | | | | | | | | |
| Vital Signs/Weight | ** | | X | | X | | X ² | X | X | X | X ² | X | | X | | |
| Physical Examination | * | | | | | | | | | X ⁴ | X | | | | | |
| Complete Neurological Exam | * | | | | | | | | | | X | | | | | |
| Height | * | | | | | | | | | | | | | | | |
| 12-lead ECG | * | | X ⁸ | | X ⁸ | | X | | | | X | | | | | |
| Blood sampling for PK | | | | | | | | | | | X ⁷ | | | | X ⁷ | |
| Chemistry/Hematology/UA | * | | | | | | X | | X | X | X | | | | | |
| CAG Repeat ¹ | * | | | | | | | | | | | | | | | |
| Blinded CYP2D6 Genotype ¹ | * | | | | | | | | | | | | | | | |
| Pregnancy Test | U | | | | | | | | | U | U | U | | | | |
| HADS | ** | | X | | X | | X | X | X | X | X | X | X | | | |
| C-SSRS ⁵ | ** | | X | | X | | X | X | X | X | X | X | X | | | |
| MoCA ⁶ | X | | | | X | | X | X | X | X | X | X | X | | | |
| UHDRS - Motor | ** | | X | | X | | X | X | X | X | X | X | X | | X | |
| UHDRS – Cognitive | X | | | | X | | X | X | X | X | X | X | X | | | |

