- ** Data (Week 13) from Study SD-809-C-15 will be utilized as part of Baseline assessment. Additional specific activities required at this visit are denoted by an “X”
- 1 Assessment transferred from Screening or Baseline evaluation in Study SD-809-C-15
 - 2 Perform orthostatic blood pressure and pulse after subject is in standing position for at least 3 minutes.
 - 3 Assessments to be completed at Investigator’s discretion
 - 4 Brief physical examination, which includes evaluation of the cardiovascular, respiratory, and abdominal systems.
 - 5 The C-SSRS Since Last Visit version is administered at all visits for Rollover subjects
 - 6 Study medication supply will be ordered (See Operations Manual for further details).
 - 7 Subjects who withdraw early from the study should have a single blood sample collected for PK at the Early Termination Visit if the last dose was within the prior 48 hours, if possible. Subjects who experience an SAE should have a single blood sample collected for metabolites of SD-809 within 48 hours of SAE, if possible.
 - 8 For subjects on allowed doses of citalopram or escitalopram:
 - Week 2: A 12-lead ECG is required at this visit.
 - Week 4: If the dose of study drug has been increased since the last ECG, a 12-lead ECG is required at this visit.
 - 9 After Week 28, perform clinic visits every 13 weeks until the End of Treatment Visit. Obtain safety labs and urine pregnancy test every 26 weeks after Week 28, and perform UHDRS-TFC every 52 weeks after Week 28.
 - 10 For subjects requiring an Unscheduled Clinic Visit for any reason, assessments denoted with X should be performed; all other assessments are as indicated at Investigator’s discretion (see Section 6.5 of the protocol).

5 Data Management

Complete details of data management will be described in a separate Data Management Plan.

6 Definition of Population

Safety Population: The Safety Population will include all subjects who were administered any study drug. Subjects who are assigned a subject number but withdrew prior to dosing will not be included in the Safety Population. If relevant, details of their participation and reason for withdrawal will be listed separately in the CSR.

Unless specified otherwise, all data will be summarized for the Safety Population. In addition, two subsets of the Safety Population are defined:

- Rollover Cohort: Successfully completed SD-809-C-15 (First-HD) prior to enrollment into SD-809-C-16 (ARC-HD)

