8.7 Comments on Statistical Analysis

The following general comments apply to all statistical analyses and data presentations:

- Unless otherwise specified, all data will be summarized separately for the Rollover Cohort and the Switch Cohort.
- Summaries will include frequencies and percentages for categorical data and the number of observations, mean, standard deviation, median, minimum, and maximum for continuous data.
- Duration variables will be calculated using the general formula: (end date – start date) + 1.
- Unless specified otherwise, for subjects in the Switch cohort, the baseline value is the last available value prior to the first administration of SD-809 on Day 1. For Rollover subjects from the First-HD study, for assessments that were scheduled to be performed at Week 13 of that study or the Baseline visit of the ARC-HD study, the baseline value is the last available off-treatment (at least 4 days after the last administration of study drug) value prior to administration of SD-809 on Day 1. For assessments that were not scheduled to be performed at Week 13 of the First-HD study or at the Baseline visit of the ARC-HD study, the baseline value is the last available value prior to administration of study drug on Day 1 of the First-HD study. For the Switch cohort, the baseline value used for calculating change from baseline for TMC and the total motor score will be the mean of the values from the Screening and Baseline visits.
- If the reported value of a clinical laboratory parameter cannot be used in a statistical summary table (e.g., a character string is reported for a parameter of the numeric type), a coded value must be appropriately determined and used in the statistical analyses. In general, a value or lower or upper limit of normal range such as '<10' or '<5' will be treated as '10' or '5', respectively, and a value such as '>100' will be treated as '100.' However, the actual values as reported in the database will be presented in data listings.
- Individual subject listings of all data represented on the eCRFs will be provided to facilitate the investigation of tabulated values and to allow for the clinical review of all data.
- Version 9.4 of SAS statistical software package will be used to provide all summaries, listings, and graphs described in this document.

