9.9.2 Vital Signs and Weight

Respiration rate (breaths/minute), temperature (°C), and weight (kg) will be obtained at each clinic visit. Supine and standing systolic and diastolic blood pressure (mmHg) and supine and standing heart rate (beats/minute) will be collected at the Baseline, Week 8, and End-of-Treatment/Early Termination visits. Seated blood pressure and heart rate will be collected at all other visits.

Weight, respiration rate, temperature, seated/supine systolic and diastolic blood pressure, and seated/supine heart rate, and the corresponding change from baseline, will each be summarized by visit using descriptive statistics.

A listing of weight and vital sign assessments will also be provided.

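### For Rollover subjects already treated with SD-809 in C-15, C-16 plans no change since first exposure for weight, vital signs, HADS and several other scales

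*SAP*

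**What the plan says.** SAP 8.7 gives each Rollover assessment a single baseline, chosen by when the assessment was scheduled.

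- If it was scheduled at C-15 Week 13 or at the C-16 Baseline visit, the baseline is "the last available off-treatment (at least 4 days after the last administration of study drug) value prior to administration of SD-809 on Day 1".
- Otherwise, "the baseline value is the last available value prior to administration of study drug on Day 1 of the First-HD study".

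SAP Table 2 (Schedule of Events B) shows which rule applies. A double asterisk means "Data (Week 13) from Study SD-809-C-15 will be utilized as part of Baseline assessment", and the row "Vital Signs/Weight" carries that mark.

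On timing, Protocol 3.1 lets subjects roll over after they "complete a one week washout and the Week 13 evaluation of Study SD-809-C-15". SAP Section 4 describes the same gap: "As Rollover subjects will have discontinued study drug (SD-809 or placebo) for at least 1 week at completion of the SD-809-C-15 study".

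On analysis, SAP 9.9.2 summarises by visit "Weight, respiration rate, temperature, seated/supine systolic and diastolic blood pressure, and seated/supine heart rate, and the corresponding change from baseline". SAP 9.9.7 summarises the rating scales as observed values, change from baseline and, for most of them, change from Week 8. By default SAP 8.7 reports by cohort, Rollover or Switch.

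Protocol 8.3 says Rollover change from baseline "will utilize the Baseline from Study SD-809-C-15 (C-15 Baseline) and the Baseline from the present study (C-16 Baseline), as appropriate", and leaves the details to the SAP. The same section says safety data will be summarised overall and by prior treatment: SD-809 ER, placebo or tetrabenazine.

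**The concern.** The study exists to describe long-term safety, and the prior-SD-809 Rollover subjects have the longest exposure. For weight, vital signs and most of the scales, their clock starts after a full course of the drug and a short break. An effect that does not reverse within about a week is then already in the baseline and is subtracted from every later change.

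Two features make this hard for a reader of the report to see. First, change from baseline would mean different things in neighbouring tables. For the same subject, cholesterol would be compared with a value before any SD-809, and weight with a value after about 12 weeks of it. Second, the default Rollover summary mixes these subjects with prior-placebo subjects, for whom the C-16 baseline does precede first exposure.

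**Working it through.** The plan states no figure to reproduce. The check traces each measure to its baseline, looks for any second analysis that fills the gap, and then sizes the omission.

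**Step 1: which baseline applies (SAP Table 2 read with SAP 8.7)**

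| Mark in Table 2 | Measures | Rollover baseline |
|---|---|---|
| ** (C-15 Week 13) | Vital signs and weight, HADS, UHDRS motor, dysarthria, SDQ, BARS, ESS | Off-treatment, before C-16 Day 1 |
| X (done at C-16 Baseline) | MoCA, UHDRS cognitive, UHDRS behaviour | Off-treatment, before C-16 Day 1 |
| * (C-15 Week 12 or earlier) | Laboratory tests, TFC, independence, functional assessment | Before C-15 Day 1 |

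**Step 2: exposure before the C-16 baseline**

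The washout takes one week and ends at Week 13, so treatment in C-15 lasted about 13 − 1 = 12 weeks. This duration is derived; neither document states it. Time off drug is nominally seven days, and SAP 8.7 accepts four or more.

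**Step 3: is there another analysis from a pre-exposure value?**

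- SAP 9.9.2 (weight, vital signs): change from the SAP 8.7 baseline only.
- SAP 9.9.7 (scales): change from the same baseline and, for most, from Week 8, which is a later origin still.
- SAP 9.9.1: exposure-adjusted adverse event rates include the C-15 active and placebo groups, but as incidence by study, not as change in weight or score.
- SAP 9.7: a split by prior C-15 treatment appears, but only for change from Week 8 in TMC and total motor score.

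No change from a pre-C-15 value is planned for the first two rows of the table.

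**Step 4: share of cumulative treatment time lying before baseline**

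For a prior-SD-809 subject at C-16 week *w*, assuming continuous dosing, the share is 12 / (12 + *w*).

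| C-16 week | Calculation | Share |
|---|---|---|
| 8 | 12/20 | 60% |
| 15 | 12/27 | 44% |
| 28 | 12/40 | 30% |
| 54 | 12/66 | 18% |
| 106 | 12/118 | 10% |

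**Step 5: effect on the means**

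Let D be the mean change from C-15 Day 1 that is still present at the C-16 baseline in prior-SD-809 subjects, and *p* their share of the Rollover cohort.

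- Prior-SD-809 mean: omits D.
- Prior-placebo mean: omits nothing, because first SD-809 exposure comes after the C-16 baseline.
- Pooled Rollover mean: omits *p* × D.

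The documents do not give the C-15 allocation. Taking *p* as 40–60% (32 to 48 of the approximately 80 planned Rollover subjects), the pooled mean omits 0.4D to 0.6D. If D were 1 kg of weight, that is 0.4 to 0.6 kg; if 2 kg, 0.8 to 1.2 kg. These values of D are illustrations only.

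**The case against.** The SAP's choice has a sound rationale. Every Rollover subject restarts at the same dose regardless of C-15 treatment (Protocol 5.2.3), and the first objective concerns titration and maintenance. An off-treatment value just before the restart is a natural reference for that. The analysis is descriptive, with no formal testing (SAP 8.1), observed values are shown by visit, and all data are listed. This stands, and it is why the C-16 baseline should remain the main one.

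A reader might infer three stronger things that the documents do not support.

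- *That the SAP contradicts the protocol on baselines.* It does not. Protocol 8.3 names both baselines, to be used as appropriate, and hands the assignment to the SAP. The SAP uses both, each for different measures.
- *That change since first exposure is estimated nowhere.* C-15 is a randomised, placebo-controlled study whose analysis plan is not before us, and change over its treatment period may well be reported there. What C-15 alone cannot give is cumulative change at, say, C-16 Week 28 or 54. Nor can C-15 and C-16 means simply be added, since only subjects who completed C-15 successfully are eligible (Protocol 3.1).
- *That the longest-exposed subjects will show the smallest change.* That needs an effect that persists through washout and then levels off, and neither document shows this for any measure. Protocol 1.2 points the other way for some: it describes short metabolite half-lives for tetrabenazine and links somnolence, akathisia and anxiety to peak concentration. Such effects may well have faded after a week off drug.

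**Conclusion.** The gap is real but limited. For weight, vital signs, HADS and the other scales under the Week 13 / C-16 rule, C-16 plans no cumulative change since first SD-809 exposure in subjects treated with it in C-15. Laboratory tests, TFC, independence and functional assessment are not affected, so the point must not be extended to all safety data.

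The size cannot be determined from the documents. It depends on D, which is unknown and could be near zero for quickly reversing effects, and on the C-15 split, which is assumed. D would also contain disease progression over the C-15 period as well as any drug effect. The practical weight of the point lies with slowly reversing measures, above all body weight.

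A separate mismatch makes it worse. Protocol 8.3 commits to safety summaries by prior treatment, while SAP 8.7 defaults to cohort, and SAP 8.10 does not list this among the changes to protocol-specified analyses. The pooled table therefore hides the subgroup in which the omission occurs.

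**What to change.** Keep the C-16 off-treatment baseline as the main one. Add to SAP 8.7, 9.9.2 and 9.9.7 a supplementary summary of change from the C-15 baseline, defined as the last value before study drug on C-15 Day 1. Apply it to weight, vital signs, HADS and every other scale with a pre-treatment C-15 value. Present it in separate columns for prior-SD-809 and prior-placebo Rollover subjects, in line with Protocol 8.3, and do not pool them.

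Use C-15 Day 1 for both columns. A reference point set at each subject's own first SD-809 dose would give the two groups calendar spans about 13 weeks apart, in a progressive disease.

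The cost is one derived variable and one table set, with no new data collection. Two caveats belong in the SAP text. First, availability should be confirmed scale by scale: the protocol refers to a C-15 baseline but does not list its contents, and MoCA and the UHDRS cognitive and behaviour parts are performed at the C-16 Baseline visit, not imported. Second, change from the C-15 baseline includes about 13 further weeks of disease progression, for which the prior-placebo column gives context.
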